### 2.5.3 Handling of missing values/censoring/discontinuations

Imputation of incomplete adverse events start and end dates follow standard conventions and are described in detail in Section [5.1.2](#).

Missing follow-up assessments for laboratory and vital signs will not be imputed.

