The appropriate personnel from the study site and Novartis will assess whether study treatment should be discontinued for any patient whose treatment code has been broken inadvertently for any reason. Study treatment must be discontinued after emergency unblinding. If discontinuation of study treatment occurs, the patient should NOT be considered withdrawn from the study. The patient should return to the clinic as soon as possible, after discontinuation of study drug, for a study treatment discontinuation visit. Treatment discontinuation visit assessments detailed in the treatment discontinuation visit (TD) in [Table 6-1](#) should be completed and recorded in the appropriate eCRF. The investigator must determine the primary reason for the patient's premature discontinuation of study treatment and record this information on the appropriate eCRF. The investigator must also contact the IRT to register the patient's discontinuation from study treatment.

During the Treatment discontinuation visit (TD), at least the following data should be collected:

- new/concomitant treatments
- adverse events/Serious Adverse Events

For patients who discontinue study treatment prematurely before the end of the treatment period for any reason other than withdrawal of informed consent, the TD visit (EOT) and Week 52 (EOS) visits must be performed.

If study drug discontinuation occurs because treatment code has been broken, refer to protocol [Section 5.5.9](#).

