Baseline	Treatment-Emergent (Confirmed ^a)	Liver-Related Clinical Symptoms ^b	Action taken	
			Monitoring ^c	Study Drug
	ALT and/or AST > 3 × baseline	With or without liver-related clinical symptoms	Comprehensive clinical evaluation and laboratory monitoring, as well as causality evaluation ^d , [REDACTED]	Permanently discontinue
Baseline normal or elevated ALT and/or AST values	ALT and/or AST > 3 × ULN and > 2 × baseline AND either total bilirubin > 2 × baseline OR INR increase by >0.3 to a value >1.5	With or without liver-related clinical symptoms	Comprehensive clinical evaluation and laboratory monitoring, as well as causality evaluation ^d , [REDACTED]	Interrupt dosing ^e
ALP				
Baseline ALP ≤ ULN	ALP > 1.5 × ULN (not due to known bone pathology)	None	Laboratory monitoring and causality evaluation ^c	Continue dosing
		Present	Comprehensive clinical evaluation and laboratory monitoring, as well as causality evaluation ^d , [REDACTED]	Interrupt dosing ^e
	ALP > 1.5 × ULN (not due to known bone pathology) AND total bilirubin > 2 × ULN ^f	With or without liver-related clinical symptoms	Comprehensive clinical evaluation and laboratory monitoring, as well as causality evaluation ^d , [REDACTED]	Interrupt dosing ^e
Baseline ALP > ULN	ALP > 2 × baseline (not due to known bone pathology)	None	Laboratory monitoring and causality evaluation ^c	Continue dosing
		Present	Comprehensive clinical evaluation and laboratory monitoring, as well as causality evaluation ^d , [REDACTED]	Interrupt dosing ^e
	ALP > 2 × baseline (not due to known bone pathology) AND total bilirubin > 2 × ULN ^f	With or without liver-related clinical symptoms	Comprehensive clinical evaluation and laboratory monitoring, as well as causality evaluation ^d , [REDACTED]	Interrupt dosing ^e

Baseline	Treatment-Emergent (Confirmed ^a)	Liver-Related Clinical Symptoms ^b	Action taken	
			Monitoring ^c	Study Drug
Total or Direct Bilirubin				
Baseline total bilirubin ≤ ULN	Total bilirubin > 2 × ULN ^f	With or without liver-related clinical symptoms	Comprehensive clinical evaluation and laboratory monitoring, as well as causality evaluation ^d , [REDACTED]	Interrupt dosing ^e
Baseline total bilirubin > ULN	Total bilirubin > 1.5 × baseline ^f	With or without liver-related clinical symptoms	Comprehensive clinical evaluation and laboratory monitoring, as well as causality evaluation ^d , [REDACTED]	Interrupt dosing ^e

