**Table 2-1 Primary variables and methods of analysis**

Variable	Method of analysis
Occurrence of adverse events	Summary table of absolute and relative frequency, overall and by preferred term
Occurrence of serious adverse events	Summary table of absolute and relative frequency, overall and by preferred term
Occurrence of adverse events resulting in discontinuation or dose reduction of study treatment	Summary table of absolute and relative frequency, overall and by preferred term
Occurrence of adverse events of special interest	Summary table of absolute and relative frequency, by type of AE as the risks are described for both tropifexor and CVC (risk definition for tropifexor are those that appear in the tropifexor IB or CVC IB, DSPP and eCRS) together with any other events identified during the course of this or other studies
Changes in vital signs	Descriptive statistics by visit
Changes in laboratory data	Descriptive statistics by visit

The statistical analysis of these variables is described in Section [2.8](#), along with the analysis of other safety variables.

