### 2.8.3 Laboratory data

The summary of safety laboratory evaluations will be presented for the groups of laboratory tests (e.g., hematology, clinical chemistry). Descriptive summary statistics for the change from baseline to each study visit will be presented. These descriptive summaries will be presented by test group, laboratory test, and treatment group. Change from baseline will only be summarized for patients with both baseline and post baseline values. Shift tables based on the normal laboratory ranges will be provided. For the shift tables, the normal laboratory ranges will be used to evaluate whether a particular laboratory test value was normal, low, or high for each visit value relative to whether or not the baseline value was normal, low, or high. These summaries will be presented by laboratory test category and treatment group.

The number and percentage of patients with new clinically notable laboratory results after baseline will be presented. Clinically notable laboratory results are listed in Section 5.3.1, for those parameters where ranges are available.

Safety laboratory parameters which are at the same time part of the efficacy analyses will be included in the safety tables as well.

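### The by-visit change and shift tables for laboratory data can understate the size of liver-test changes in an arm with more Table 14-1 stops; add worst-value and last on-treatment summaries

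*SAP*

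**What the plan says.** SAP Table 2-1 lists changes in laboratory data among the primary variables and gives one method, "Descriptive statistics by visit". SAP 2.8.3 fills this in: "Descriptive summary statistics for the change from baseline to each study visit will be presented", and "Change from baseline will only be summarized for patients with both baseline and post baseline values". The shift tables "evaluate whether a particular laboratory test value was normal, low, or high for each visit value". SAP 2.5.3 adds "Missing follow-up assessments for laboratory and vital signs will not be imputed". Protocol 9.4.4 plans no sensitivity analysis for the primary variables, and SAP 2.5.4 adds only COVID-19 analyses.

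Protocol Appendix 2, Table 14-1, requires permanent discontinuation of study drug on the laboratory value itself. With baseline ALT/AST below 2 x ULN, the trigger is a value above both 3 x ULN and 5 x baseline. With a higher baseline it is "ALT and/or AST > 3 × baseline".

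For patients who stop early, Protocol 5.6.2 says "the TD visit (EOT) and Week 52 (EOS) visits must be performed". Protocol Section 6 instead requires the planned Week 48 visit and the Week 52 visit. Table 6-1 puts Week 48 and the treatment-discontinuation (TD) visit in one column.

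**The concern.** Whether a patient contributes to a later row can depend on the value being summarised. A patient whose ALT crosses a Table 14-1 threshold stops drug and need not attend the remaining intermediate visits. The scheduled value that triggered the stop stays in its own row. Later rows lose the patient, and a higher value at the confirmatory draw, 48 to 72 hours after the result is available, belongs to no scheduled visit. Stops at different times also spread the triggering values over several rows.

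The objective compares each combination with each monotherapy over 48 weeks, and Protocol 1.1 itself foresees a possible additive effect of the two drugs on transaminases. If a combination arm had more liver stops, its later rows would describe mainly those who tolerated the drug. The size of its ALT, AST and bilirubin changes would be understated where the comparison matters most.

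The visible SAP has no worst-value summary, no last on-treatment summary, and no rule assigning an early TD result to an analysis visit. A Week 48 row could therefore hold on-treatment values, early values near a peak, recovered off-drug values, or a mixture.

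**Working it through.** The plan states no figure for this variable, so there is nothing to reproduce. The check is an illustration of how the tables behave.

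**Inputs.** From the documents: about 50 patients per arm, and the Table 14-1 threshold of 5 x baseline for a baseline below 2 x ULN. Assumed: baseline ALT 1 x ULN; mean change of -0.3 x ULN in patients who stay; last on-treatment change *d* of +4 to +6 x ULN in those who stop (+4 corresponds to the 5 x baseline threshold); *m* stoppers absent from the later visit.

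**Formulas.** The observed-only mean is -0.3 for any *m*. The mean with the last on-treatment value kept is [(50 - m)(-0.3) + m·d]/50. For m = 5 this is (-13.5 + 20)/50 = +0.13 with d = 4, and (-13.5 + 30)/50 = +0.33 with d = 6.

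| Stopped, of 50 | Observed-only mean (n) | Last on-treatment value kept | Share in the liver-event table |
|---|---|---|---|
| 1 | -0.30 (49) | -0.21 to -0.17 | 2% |
| 2 | -0.30 (48) | -0.13 to -0.05 | 4% |
| 5 | -0.30 (45) | +0.13 to +0.33 | 10% |
| 10 | -0.30 (40) | +0.56 to +0.96 | 20% |

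**The same in U/L.** Assume baseline 60 U/L, a change of -15 in stayers, and stops at 3 or 5 times baseline. These multiples belong to the two baseline strata of Table 14-1, so only one applies to a given patient. The mean is (1 - p)(-15) + p·60(k - 1), with p the proportion stopping and k the multiple.
- p = 2.5%: -14.625 + 3 = -11.6, or -14.625 + 6 = -8.6.
- p = 10%: -13.5 + 12 = -1.5, or -13.5 + 24 = +10.5.
- Between-arm difference lost at 10% versus 2.5%: 0.075 x (120 + 15) = 10.1, or 0.075 x (240 + 15) = 19.1 U/L.

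Only the 2.5% comes from the documents. It is the share of the CVC/CVC group that discontinued for increased ALT in the two-year CENTAUR study (Protocol 1.1). The 10% and all the U/L inputs are assumptions.

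**Which rows this applies to.** It applies to a later visit from which the stoppers are absent. For Week 48 it applies only if early TD values and post-discontinuation Week 48 values are kept out of that row, which the documents do not settle.

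**The case against.** The strongest reply is that the plan already shows these patients elsewhere. SAP 2.8.1 gives, per arm, the frequency of Appendix 2 liver and Appendix 3 renal events. SAP 5.3.1 counts them on laboratory criteria alone, without requiring confirmation. A patient stopped under Table 14-1 meets an Appendix 2 criterion by definition. Adverse events leading to discontinuation and events of special interest are themselves primary variables, and SAP 2.3 tabulates disposition with reasons. SAP 2.1 also reports medians and quartiles, which a few extreme values move far less than means. There is no hypothesis, and SAP Section 3 says the judgement rests on the whole safety profile.

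Most of this stands. A reader might infer that the arm with most liver stops would look as good as the others on safety. The documents do not support that: the last column of the table above shows the excess in plain sight. A reader might also infer that stoppers leave the study. Protocol 5.6.2 says stopping drug is not withdrawal, and Protocol 7.3 keeps liver stoppers under close follow-up until values settle. Nor is declining to impute safety laboratory values an error.

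The reply does not supply the size of change. Event counts and disposition are counts. SAP Table 5-1, which defines notable values, has no threshold for ALT, AST, ALP or bilirubin. Under Protocol 7.1 a laboratory abnormality becomes an adverse event only if it causes symptoms, is clinically significant or needs therapy. The table shells and the sponsor's internal liver analysis plan might contain worst-value tables, but the SAP text does not commit to them.

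**Conclusion.** The point holds for the by-visit change and per-visit shift tables, and not for the safety comparison as a whole. These tables can understate the size of transaminase and bilirubin changes in an arm with more permanent liver stops, and can miss peaks at unscheduled draws. The other planned outputs would reveal the excess of patients but not how far their values moved.

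The size depends on unequal stopping, for which the documents give no data by arm, and on assumed ALT values. On those assumptions, one or two stoppers in 50 shift the mean by about 0.1 to 0.25 x ULN, and five shift it by 0.43 to 0.63 x ULN. The 10 to 19 U/L contrast should not be read as a prediction that the Week 48 row will show no difference, for the reason given in the working.

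Extending the argument to renal stops is also tempting but weak. Table 15-1 asks the investigator only to consider interruption or discontinuation, while Protocol 5.6.2 lists specified renal events among reasons for mandatory discontinuation. Those passages must be reconciled before anything is built on them. This is a worthwhile, inexpensive improvement.

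**What to change.** In SAP 2.8.3:
- Keep the by-visit tables without imputation and show the number of patients contributing at each visit, by arm.
- Add, per arm and parameter, change from baseline to the worst and to the last on-treatment value, using scheduled, unscheduled and TD-visit results. Define worst as the maximum, or the minimum where low is adverse.
- Add a shift table from baseline category to worst post-baseline category and make it the lead shift table.
- State that an early TD result is not tabulated as Week 48.

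In the protocol, reconcile 5.6.2 with Section 6 on whether early stoppers have a TD visit, a planned Week 48 visit, or both. Reconcile 5.6.2 with Table 15-1 on renal events.

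The cost is some SAP wording and a few standard tables from data already collected. Worst-value summaries lie above typical values in every arm, so they should be read only as comparisons between arms.

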### 2.5.4 Supportive analyses

Supportive analyses are added for evaluation of the impact of COVID-19 on study results. See [Section 2.8.1](#).

## 2.6 Analysis of the key secondary objective

There is no key secondary objective defined in the protocol.

## 2.7 Analysis of secondary efficacy objective(s)

### 2.7.1 Secondary endpoints

There is a single secondary objective in this study which is to characterize the efficacy of tropifexor + CVC in patients with NASH with fibrosis stage F2/F3 as assessed by histological improvement after 48 weeks of treatment compared to monotherapies (tropifexor and CVC) relative to baseline biopsy. There are two endpoints that will be used to evaluate this objective:

- Proportion of patients who have at least a one-point improvement in fibrosis
- Proportion of patients with resolution of steatohepatitis

The determination of fibrosis improvement will be based on NASH CRN staging (see [Table 2-2](#)). Only main stages (0, 1, 2, 3, and 4) will be considered. For example, a change from 1c to 1b or 1a will not be counted as a one-point change.

**Table 2-2 Fibrosis score according to NASH CRN**

Fibrosis score	Histopathology
0	none
1a	mild perisinusoidal fibrosis
1b	moderate perisinusoidal fibrosis
1c	portal/periportal fibrosis only
2	perisinusoidal and periportal fibrosis
3	bridging fibrosis
4	cirrhosis

Results of the paired biopsy readings will be used for all biopsy-based outputs, yet not retrospectively for re-evaluation of patient eligibility at screening, which is performed based on real-time biopsy reading.

Resolution of steatohepatitis will be determined as diagnostic category “not NAFLD” or “NAFLD, not NASH” as provided in the central biopsy report.

### 2.7.2 Statistical hypothesis, model, and method of analysis

The two secondary endpoints are incorporated in two estimands.

The first estimand is defined as below:

- Treatment: The randomized treatment (tropifexor 140 µg once-daily, CVC 150 mg once-daily, tropifexor 140 µg + CVC 150 mg once-daily, and tropifexor 90 µg + CVC 150 mg once-daily) taken for 48 weeks, further defined in Section 5.2 in the protocol.
- Population: Full analysis set.
- Endpoint: Proportion of patients who have at least a one-point improvement in fibrosis.
- Summary measure: Difference in the proportion of patients on the different tropifexor + CVC regimens who achieve at least a one-point improvement in fibrosis at Week 48 biopsy compared to tropifexor and CVC monotherapy patients.

The second estimand is the same as the first one except

- Endpoint: Proportion of patients with resolution of steatohepatitis

- Summary measure: Difference in the proportion of patients on the different tropifexor + CVC regimens who achieve resolution of steatohepatitis at Week 48 relative to baseline compared to tropifexor and CVC monotherapy patients.

Both estimands will be evaluated using a Cochran-Mantel-Haenszel test controlling for baseline fibrosis stage (F2/F3). Risk differences and odds ratios with 95% confidence intervals will provide supporting information for both estimands.

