### 3.2 Power considerations with given sample size for efficacy assessment

To evaluate the effectiveness of tropifexor + CVC with respect to the proportion of patients who have at least a one point improvement in fibrosis at Week 48 compared to baseline (i.e, the response rate), one needs to consider the effect size that one is able to detect with respect to both tropifexor and CVC as monotherapy.

- For CVC, based on information from the CENTAUR Phase 2b study, Friedman (2017), it can be assumed that the monotherapy response rate at Week 48 in F2/F3 patients would be approximately 35%
- For tropifexor, a response rate of 42% is assumed (best-case scenario) based on the interpolation of expected Week 72 response rate and assuming linear improvement over time
- For the combined effect of tropifexor + CVC it will be assumed that 75% of the efficacy for CVC will be added to the effect of tropifexor (i.e. a response rate of  $42 + 0.75 \cdot 35 = 69\%$ )

For comparisons between tropifexor + CVC and CVC monotherapy a 2-group continuity corrected  $\chi^2$  test of proportions with type I error rate of 0.10 (2-sided, no adjustment for multiple comparisons), a sample size of 50 per group results in a power of 95% (nQuery Advisor 7.0).

For comparisons between tropifexor + CVC and tropifexor monotherapy a 2-group continuity corrected  $\chi^2$  test of proportions with type I error rate of 0.10 (2-sided, no adjustment for multiple comparisons), a sample size of 50 per group results in a power of 81% (nQuery Advisor 7.0).

Further scenarios assuming different response rates for tropifexor and the magnitude of effect added to tropifexor by CVC are described in [Table 3-1](#).

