**Table 3-1 Power for detecting a treatment difference between tropifexor + CVC and tropifexor and CVC monotherapy**

Assumed tropifexor response rate	Assumed response rate of tropifexor + CVC	Power N = 50/arm vs. tropifexor monotherapy	Power N = 50/arm vs. CVC monotherapy
Current target 42% response rate at Week 48 (50% improvement over OCA)	½ effect of CVC added to tropifexor ((60%)	48%	75%
	¾ effect of CVC added to tropifexor (69%)	81%	95%
	Full effect of CVC added to tropifexor (77%)	96%	99%
Response rate between target and OCA at Week 48 (35%)	½ effect of CVC added to tropifexor (53%)	48%	48%
	¾ effect of CVC added to tropifexor (62%)	81%	81%
	Full effect of CVC added to tropifexor (70%)	96%	96%
Worst case: tropifexor same effect as OCA 28% at Week 48	½ effect of CVC added to tropifexor (46%)	50%	23%
	¾ effect of CVC added to tropifexor (55%)	82%	56%
	Full effect of CVC added to tropifexor (63%)	96%	81%

\*Power calculated assuming a two-sided Type I error rate of 0.10

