## 5.6 Other statistical aspects

### Secondary efficacy endpoints

Multiple imputation is adopted to impute missing Week 48 biopsy results for eligible patients. See Section 5.1.4 for more details.

CMH test is adopted for inference controlled for the baseline fibrosis stage (F2/F3). In order to pool results from multiple imputation, test statistic of CMH test is transformed using Wilson-Hilferty transformation

$$ST_{WH\_CMH^{(m)}} = \frac{\sqrt[3]{CMH^{(m)}/df} - (1 - \frac{2}{9 * df})}{\sqrt[2]{2/(9 * df)}}$$

Where  $CMH^{(m)}$  is the CMH test statistic computed from the  $m$ -th imputed dataset,  $df$  is the degrees of freedom associated with the test statistic, and  $ST_{WH\_CMH^{(m)}}$  follows approximately standard normal distribution. Consequently, the test results obtained from multiple imputation datasets can be combined by specifying the model effects and standard error in PROC MIANALYZE in SAS and the final one-side  $p$ -value for CMH test can be obtained.

Odds ratio and relative risk obtained from PROC FREQ also need to be transformed to normal distribution before pooling. Both statistics are log-normally distributed and hence a simple log transformation would transform them to normal and similar procedure to the above can be followed to obtain the pooled results. Finally, exponential transformation is implemented to transform the statistics and their CI back to the original scale.

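### SAP 5.6 calls the pooled CMH p-value one-sided, but it is the ordinary two-sided CMH p-value, and no efficacy section says at what level it is read

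*SAP*

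**What the plan says.** Three parts of the SAP bear on how the secondary efficacy result is read.

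- **Analysis (2.7.2; Protocol 9.5.1 and Table 9-2 agree).** Both estimands use a CMH test controlling for baseline fibrosis stage. Of the effect estimates the SAP says: "Risk differences and odds ratios with 95% confidence intervals will provide supporting information for both estimands". No level or sidedness is given for the CMH p-value.
- **Power (3.2 and Table 3-1; Protocol 9.8.2 agrees).** The test is a "2-group continuity corrected" chi-square with "type I error rate of 0.10 (2-sided, no adjustment for multiple comparisons"). The table footnote repeats the level: "Power calculated assuming a two-sided Type I error rate of 0.10". Against tropifexor, "a sample size of 50 per group results in a power of 81% (nQuery Advisor 7.0"); against CVC, "a sample size of 50 per group results in a power of 95% (nQuery Advisor 7.0").
- **Pooling (5.6, Secondary efficacy endpoints).** The CMH statistic from each imputed dataset is put through a Wilson-Hilferty transformation and treated as approximately standard normal. The results are then combined "in PROC MIANALYZE in SAS and the final one-side" p-value for the CMH test is obtained.

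Two statements limit the weight of all this. SAP 2.5.2 says that the study has no pre-specified hypotheses, and SAP 3 says that the sample size rests on feasibility.

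**The concern.** For a comparison of two treatments, a one-sided p-value normally means evidence in one direction, and its usual threshold is half the two-sided level. With power stated at two-sided 0.10, a reader who trusts the label in SAP 5.6 would compare the p-value with 0.05 and take a small value as favouring the combination.

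Neither step fits the quantity that 5.6 defines. If it is in fact the two-sided p-value, comparing it with 0.05 applies a stricter test than the one powered, and a small value is equally compatible with a worse combination. No efficacy section states a level that would settle the reading. Protocol 1.2 says the data will be used to judge whether further development of the combination is beneficial, so the reading is not purely academic.

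**Working it through.** **Inputs.** From SAP 3.2: 50 per arm, tropifexor 42%, combination 69%, and for CVC a "monotherapy response rate at Week 48 in F2/F3 patients would be approximately 35"%. The transformation is from SAP 5.6, with 1 degree of freedom for a two-arm comparison.

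**1. Reproduce the stated power.** The continuity correction is applied through an effective sample size n′ = n(1 − 1/(nd))², where d is the difference in rates. Power = Φ{[d√n′ − z√(2p̄q̄)] / √(p₁q₁ + p₂q₂)}, with z = 1.645 for two-sided 0.10.

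- Against tropifexor: d = 0.27, n′ = 42.87, d√n′ = 1.768, √(2p̄q̄) = 0.703, denominator 0.676. (1.768 − 1.645 × 0.703)/0.676 = 0.904, so power is 81.7% (stated 81%).
- Against CVC: d = 0.34, n′ = 44.29, d√n′ = 2.263, √(2p̄q̄) = 0.707, denominator 0.664. The ratio is 1.657, so power is 95.1% (stated 95%).

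Both stated figures reproduce.

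**2. What the transformed statistic measures.** With df = 1 the formula in SAP 5.6 is W = (Q^(1/3) − 7/9)/√(2/9), where Q is the CMH chi-square.

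| Q | Two-sided CMH p | Q^(1/3) | W | Upper tail of W |
|---|---|---|---|---|
| 2.706 | 0.10 | 1.394 | 1.306 | 0.096 |
| 3.841 | 0.05 | 1.566 | 1.672 | 0.047 |

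The upper tail of W is the two-sided CMH p-value to within about 0.004. Taking one tail of W is the correct computation; both tails at Q = 2.706 would give 0.19. Only the tail of W is one-sided. The treatment comparison is not, because Q is a square and carries no sign.

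**3. Direction.** In 40,000 simulated trials with equal rates (42% in both arms, 25 per arm in each of two strata, complete data), the upper-tail p was below 0.10 in 10.2%. In 5.2% the combination was also the worse arm, so about half of the small p-values pointed the wrong way. With the combination truly worse (22% against 42%, 48 per arm), the p-value was below 0.05 in 57% of trials, essentially all with the combination worse.

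**4. Read at 0.10.** Simulated power of the upper-tail p-value at 69% against 42% and against 35% (50 per arm, two equal strata) is 86% and 96%. The uncorrected formula gives 86.7% and 96.9%. The stated 81% and 95% describe this p-value at 0.10, slightly conservatively because of the continuity correction.

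**5. Read at 0.05.** Step 1 with z = 1.960 gives:

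- Against tropifexor: (1.768 − 1.960 × 0.703)/0.676 = 0.577, so 71.8%.
- Against CVC: the ratio is 1.321, so 90.7%.

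Without the continuity correction the figures are 78.4% and 93.8%. The simulated CMH p-value is below 0.05 in 80% and 94%.

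**6. Trials whose reading changes.** These are trials with p between 0.05 and 0.10. In a two-stratum simulation with 48 per arm (193 randomized patients over four arms, Protocol Amendment 3), the share is about 9% at 69% against 42% and 13% at 62% against 42%. With 50 per arm it is about 6% and 9%. The spread comes from the discreteness of the counts.

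**The case against.** The best reply is that the phrase in SAP 5.6 is a computing instruction. PROC MIANALYZE treats the pooled value as normal, one tail has to be taken, and the text says which. It does not call the result a superiority test or tie it to 0.05. This stands as far as the computation goes, but the sentence attaches the word to the p-value of the CMH test, and no other section corrects the impression.

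A second reply is that direction is already visible, since risk differences and odds ratios with intervals accompany the p-value. This also stands. In the 22% against 42% case, no trial with p below 0.05 and the combination worse had a Wald 95% interval that included zero. A worse combination would not pass unnoticed in a full report; the risk is to a p-value quoted on its own.

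Third, a 95% interval beside power at 0.10 is not in itself an error. The intervals are labelled as supporting information, the sample size is not power-based, and no decision rule is set.

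A reader might go further and infer that, with three different conventions in play, the stated power belongs to none of the reported results. The documents do not support that: the pooled p-value read at 0.10 is the result that the power describes (step 4). Nor should 72% and 91% be taken as the chance that the planned intervals exclude no difference. SAP 5.6 prescribes asymptotic limits under multiple imputation, for which the uncorrected 78% and 94% are closer.

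**Conclusion.** The point holds as a mislabel plus an omission. SAP 5.6 names a non-directional p-value one-sided, and no efficacy section gives its level. Read two-sided at 0.10, it agrees with the stated 81% and 95%. Read at its label against 0.05, the like-for-like power is about 72% and 91%, and roughly 6% to 9% of trials at 69% against 42% would be read differently (9% to 13% at 62% against 42%).

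The consequence is moderate, because the estimates show direction and the study has no pre-specified hypotheses. The figures assume complete data, equal strata with a common response rate and the plan's assumed rates. The equivalence in step 2 was checked on single datasets, not after pooling over the 50 imputations. The loss of sign does not depend on that, since each statistic is squared before it is pooled.

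**What to change.** 1. In SAP 5.6, replace the one-side wording: the upper tail of the pooled, transformed statistic gives the two-sided CMH p-value, and it is reported with the sign of the risk difference.
2. In SAP 2.7.2, state that the CMH p-value is read two-sided at 0.10 without multiplicity adjustment, the level used for the power figures.
3. In the same place, note that the 95% intervals are supporting information and are not tied to the 0.10 level. Adding 90% intervals is optional.

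The stated power needs no replacement. The cost is two or three sentences in the SAP before unblinding, with no change to data, design or programming beyond a table label.
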